9.2.1. Study Stopping Rules

If Pacira, the investigator, or officials from regulatory authorities discover conditions during the study that indicate that the study or study site should be terminated, this action may be taken after Pacira has consulted with appropriate regulatory authorities and notified the investigator(s).

The Pacira Medical Monitor and Pharmacovigilance team review all serious adverse events (SAEs) reported from Pacira clinical studies on an ongoing basis and in real time (i.e., as the events are reported). The Medical Monitor is responsible for temporarily pausing the study if the type, frequency, or seriousness/severity of such events suggests a potential threat to the safety of the study subjects. If such action is taken, a thorough review of all available data will be performed. Based on the results of this review and discussions with investigators and/or regulatory authorities, the study may be restarted or permanently terminated as warranted.

This trial design also includes efficacy stopping rules using group sequential design stopping rules as described in [Section 15.8](#).

In addition, any death will be thoroughly reviewed, and appropriate action taken.

9.3. Discussion of Study Design

This phase 3, multicenter, double-blinded, randomized, active controlled study will enroll approximately 120 subjects to evaluate the efficacy and safety of EXPAREL, EXPAREL admixed with 0.25% bupivacaine HCl and 0.25% bupivacaine HCl when administered as a combined sciatic (in the popliteal fossa) and saphenous (in the adductor canal) nerve blocks, in subjects undergoing lower extremity surgeries.

Only Cohort 1 subjects, 60 subjects all undergoing bunionectomy surgery, will provide blood samples for PK assessments. Subjects in this cohort will provide information on efficacy and safety of EXPAREL, EXPAREL admixed with 0.25% bupivacaine HCl, and 0.25% bupivacaine HCl.

Cohort 2 will assess the efficacy and safety of EXPAREL, EXPAREL admixed with 0.25% bupivacaine HCl, and 0.25% bupivacaine HCl in 60 subjects undergoing lower extremity surgery.

The three treatment arms of the study for Cohort 1 and 2 are as follows:

- **EXPAREL arm:** subjects randomized to this treatment arm will receive 20 mL (266 mg) EXPAREL mixed with 20 mL saline.
- **EXPAREL admix arm:** subjects randomized to this treatment arm will receive 20 mL (266 mg) EXPAREL admixed with 20 mL (50 mg) 0.25% bupivacaine HCl.
- **Bupivacaine HCl arm:** subjects randomized to this treatment arm will receive 40 mL (100 mg) 0.25% bupivacaine HCl.

For all arms, the total volume (40 mL) will be split such that 20 mL will be administered as the sciatic nerve block (in popliteal fossa) and 20 mL will be administered as the saphenous nerve block (in the adductor canal).

10. STUDY POPULATION

Approximately 120 adult subjects undergoing lower extremity surgeries will be enrolled for the study. The surgeries that can be included in the study are:

1. Bunionectomy
2. 1st metatarsophalangeal fusion
3. Specific forefoot surgeries (Weil osteotomy, Clayton-Hoffman procedures only)
4. Midfoot fusion
5. Hindfoot fusion
6. Total ankle arthroplasty

10.1. Inclusion Criteria

At screening, the subject should satisfy the following criteria:

1. Healthy adult male or female volunteers ages 18 or older
2. American Society of Anesthesiologists (ASA) physical status 1, 2, or 3 (see Appendix 6, [Section 18.6](#))
3. Able to provide informed consent, adhere to the study schedule, and complete all study assessments
4. Body Mass Index (BMI) ≥ 18 and ≤ 40 kg/m²

10.2. Exclusion Criteria

At screening, the subject must not meet any of the following criteria:

1. Allergy, hypersensitivity, intolerance, or contraindication to any of the study medications for which an alternative is not named in the protocol (e.g., amide-type local anesthetics, opioids, bupivacaine HCl, nonsteroidal anti-inflammatory drugs [NSAIDs])
2. Concurrent painful physical condition that may require analgesic treatment (such as long-term, consistent use of opioids) in the post dosing period for pain and which, in the investigator's opinion, may confound the post dosing assessments
3. History of, suspected, or known addiction to or abuse of illicit drug(s), prescription medicine(s), or alcohol within the past 2 years
4. Administration of an investigational drug within 30 days or 5 elimination half-lives of such investigational drug, whichever is longer, prior to study drug administration, or

planned administration of another investigational product or procedure during the subject's participation in this study

5. Previous participation in an EXPAREL study
6. Uncontrolled anxiety, schizophrenia, or other psychiatric disorder that, in the opinion of the investigator, could interfere with study assessments or compliance
7. Currently pregnant, nursing, or planning to become pregnant during the study
8. Clinically significant medical disease that, in the opinion of the investigator, would make participation in a clinical study inappropriate. This includes diabetic neuropathy, coagulation or bleeding disorders, severe peripheral vascular disease, renal insufficiency, hepatic dysfunction or other conditions that would constitute a contraindication to participation in the study
9. Currently on a neuromodulating agent (e.g., gabapentin, pregabalin [Lyrica], duloxetine [Cymbalta], etc.)
10. Inadequate sensory function on the foot (monofilament test)
11. Chronic opioid use within 30 days prior to randomization (average ≥ 30 oral morphine equivalents/day)

Given the COVID-19 pandemic, if there is a concern about a subject's recent or potential exposure to COVID-19, or if the subject is not medically fit/cleared for surgery due to suspected COVID-19 illness/symptoms, the subject must be excluded per Exclusion criterion #8.

10.3. Removal of Subjects from Therapy or Assessment

Every reasonable effort will be made to maintain subject compliance and participation in the study. Reasons for discontinuation of any subject from the study will be recorded.

If any clinically significant event or condition is uncovered during the study period (e.g., excessive bleeding, acute sepsis) that might render the subject medically unstable or compromise the subject's postsurgical course, the subject should be withdrawn from the study and the event or condition should be reported as an AE or SAE.

If a subject withdraws from the study and has an ongoing AE, every effort must be made to follow up on such events until satisfactory resolution is obtained or further follow-up is otherwise no longer warranted.

10.3.1. Withdrawal Secondary to Adverse Events

If a subject experiences an AE that renders the subject incapable of continuing with the remaining assessments, the subject will be discontinued from further participation in the study. A final evaluation, including the End of Study assessments (see [Section 10.3.3](#)), should be performed so that the subject's study participation can be terminated in a safe and orderly manner.

Any subject who discontinues because of an AE should be instructed to notify the study personnel of any abnormal symptoms and to come to the study site if medical evaluation is needed and the

urgency of the situation permits. Any subject exhibiting AEs will receive appropriate treatment at the discretion of the investigator until resolution of the AE.

For emergencies and other unscheduled visits to a medical facility other than the study site, medical records must be obtained by the investigator and appropriate information captured in the subject's case report form (CRF).

In addition, the subject may be withdrawn from the study if the subject meets the following criterion during or after the surgery:

Any clinically significant event or condition uncovered during the surgery (e.g., excessive bleeding, acute sepsis) that, in the opinion of the investigator, renders the subject medically unstable or complicates the subject's postsurgical course.

10.3.2. Voluntary or Study Investigator Withdrawal

Subjects are free to discontinue from the study at any time, without prejudice to future treatment. A subject may be discontinued from the study if the subject refuses study treatment (i.e., combined sciatic [in the popliteal fossa] and saphenous [in the adductor canal] nerve blocks) or refuses to comply with study procedures. Subjects should be encouraged to complete the study safety assessments. Reasons for discontinuation from the study will be recorded.

If a subject is discontinued by the investigator or voluntarily withdraws from the study after receiving the study drug, the subject will be asked to complete a final evaluation, including the early termination assessments (see [Section 10.3.3](#)), so that the subject can be withdrawn in a safe and orderly manner.

After termination from the study, the subject may be followed for safety including monitoring of AEs through POD 14.

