9.2. Duration of the Study and Subject Participation

Participation will begin upon signing of the ICF. No more than 30 days should pass between signing the ICF and study drug administration. Study drug administration will be on the same day of surgery. A follow-up phone call will occur on Post-operative Day (POD) 14 (± 3 days). Therefore, each subject may participate in the study for up to a maximum of 47 days.

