10.3.3. Early Termination Assessments

In case of early termination, the following assessments shall be performed:

- Record date and time of withdrawal
- Record responses to pain assessment:
 - Pain intensity scores on the Numeric Rating Scale (NRS) measured as “How much pain are you experiencing right now?”
 - Pain intensity scores (using the NRS) measured as “What was your worst pain in the last 24 hours?”
 - Pain intensity scores (using the NRS) measured as “What was your average pain in the last 24 hours?”
- Remind to return the e-diary (if applicable)
- Final phone call for safety

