11.7. Postsurgical Pain Medication for Breakthrough Pain

An unscheduled pain intensity assessment using the NRS (measured as “How much pain are you experiencing right now?”) must be completed immediately prior to administration of any breakthrough pain medication up to 96 hours post-surgery. All opioid and other analgesics (pain medications) administered post-surgery through POD 14 must be recorded.

Medications will be provided on an as needed (PRN) basis in relation to the breakthrough pain intensity. The intent is to use the guide below in a step-wise approach; acetaminophen or NSAIDs should be used for the initial treatment of post-surgical pain and escalation to opioids (and subsequent increased dose of opioids) should be implemented if the initial pain treatment (and initial opioid dose) is insufficient for pain relief. Opioids should not be the first choice for pain relief unless clinically indicated in the opinion of the investigator and should not be given on a schedule.

- For the initial treatment of post-surgical pain, subjects may receive either acetaminophen or NSAIDs without exceeding the maximum daily dose.
- If the initial pain treatment (acetaminophen or NSAIDs) is insufficient for pain relief, immediate release PO oxycodone may be administered in a stepwise approach:
 - Initial dose of 5 mg oxycodone may be offered;
 - If the initial opioid dose is insufficient for pain relief, 10 mg oxycodone may be offered.
- If a subject is unable to tolerate PO medication or the PO oxycodone pain relief is insufficient, IV morphine (initiated at 2 mg) or hydromorphone (initiated at 0.2 mg) may be administered.

Post discharge, the subject may be provided with a prescription for oxycodone 5 mg. The subject may take acetaminophen, NSAIDs, or the prescribed oxycodone and will be given instructions on which medication to take PRN based on their pain intensity.

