11.8. Treatment Compliance

Not applicable, since study drug (EXPAREL, EXPAREL admix, or bupivacaine HCl) will be administered preoperatively by the study staff.

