13.1. Instructions for Conducting Procedures and Measures

All PK, sensory/motor function assessments, and safety assessments conducted after baseline (predose) will be timed from the end of the block. End of block procedure is defined as the time of completion of study drug administration after combined sciatic (in popliteal fossa) and saphenous (in the adductor canal) nerve blocks.

At timepoints when multiple assessments coincide, assessments will be performed in the following sequence: pain intensity assessment, sensory assessments, motor assessment, blood draw for PK assessment as applicable.

The **start of surgery** is defined as the time of the first incision. The **end of surgery** is defined as the time recorded in the surgical record. **Postsurgical** is defined as after the end of surgery.

Postsurgical analgesia and collection of study data through the primary endpoint will take place under the supervision of study staff at the site.

Subjects will be provided an e-diary on the day of surgery and instructed on duties and responsibilities with the e-diary.

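### Withdrawal after the single block ends scheduled pain scoring even for subjects who can still report pain; the likely effect is small and a few sentences would fix it

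*Protocol*

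**What the plan says.** - **Dosing.** Under Protocol 11.8, study drug "will be administered preoperatively by the study staff". It is given once.
- **Withdrawal for complications.** Protocol 10.3 first asks sites to work to keep subjects in the study. It then says that, for a clinically significant event that might destabilise the subject or compromise the postsurgical course, "the subject should be withdrawn from the study and the event or condition should be reported as an AE or SAE". Ability to report pain is not a condition.
- **Withdrawal for inability.** Protocol 10.3.1 is a separate rule: after "an AE that renders the subject incapable of continuing with the remaining assessments, the subject will be discontinued from further participation". For events uncovered during surgery, the same section is only permissive and leaves the judgement to the investigator.
- **What is collected at termination.** The required list in Protocol 10.3.3 has one set of pain scores (current, worst and average), an e-diary reminder and a "Final phone call for safety", for which no date is given.
- **Safety after termination.** Protocol 10.3.2: "After termination from the study, the subject may be followed for safety including monitoring of AEs through POD 14". Protocol 14.1.2 makes AE recording through POD 14 mandatory and does not exempt withdrawn subjects.
- **Setting.** Protocol 13.1: "collection of study data through the primary endpoint will take place under the supervision of study staff at the site". Protocol 11.7: "All opioid and other analgesics (pain medications) administered post-surgery through POD 14 must be recorded".
- **Analysis.** Protocol 15.4 keeps every randomized subject who has the planned surgery in the efficacy set. SAP 9.2.2 gives scores inside an opioid window the worst observed value. It imputes the remaining gaps by MCMC within arm, and the model holds only the 16 scheduled NRS points.

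**The concern.** Once the block is in, there is no study drug to discontinue. Withdrawing a subject who can still give a pain score therefore gives up primary-endpoint data that site staff are already in place to collect.

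The missing scores are then imputed as if, given the earlier scores, the complication that led to withdrawal told us nothing more about later pain. That is doubtful for these subjects. If the complication raises pain beyond what the earlier scores predict, the imputed values are too low. In the bupivacaine arm this shrinks the observed difference and costs power. In the EXPAREL arm it favours EXPAREL, because SAP 9.5.1 declares superiority when the upper confidence bound for EXPAREL minus bupivacaine is below 0.

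The sections also disagree with each other. For events uncovered during surgery, 10.3 says *should* and 10.3.1 says *may*. For AEs after withdrawal, 10.3.2 says *may* and 14.1.2 says *must*.

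**Working it through.** **1. The plan's own figure.** Inputs from Protocol 15.3: 40 per arm, SD 170, difference 150, two-sided alpha 0.05.

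- SE = 170 × √(2/40) = 38.01.
- Two-sample t-test, 78 df: power = 97.4%. The stated *at least 90%* is true, with margin.
- Power of 90% needs a difference of 124.8, so 150 − 124.8 = 25.2 units can be lost before power falls below 90%.

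**2. Scheduled scores lost per withdrawn subject.** There are 16 points, one every 6 h to 96 h. Points remaining after withdrawal at time T are (96 − T)/6:

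| Withdrawn at | Points lost |
|---|---|
| 24 h | 12 |
| 48 h | 8 |
| 72 h | 4 |

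**3. Shift in one arm's mean AUC.** If k of 40 subjects withdraw at T and true later pain exceeds the imputed values by g NRS points, the arm mean is understated by k × (96 − T) × g / 40. The documents give neither a withdrawal rate nor a pain gap, so k = 1 to 3, T = 24 to 72 h and g = 1 to 2 are assumptions.

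- Low: 1 × 24 × 1 / 40 = 0.6 units = 0.4% of 150 = 0.016 SE.
- High: 3 × 72 × 2 / 40 = 10.8 units = 7.2% of 150 = 0.284 SE.

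**4. Effect on the primary test, all withdrawals in one arm.**

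| Shift | Power, if in the bupivacaine arm | Chance of declaring superiority with no true difference, if in the EXPAREL arm |
|---|---|---|
| 0 | 97.4% | 2.5% |
| 0.6 | 97.3% (difference 149.4) | 2.6% |
| 10.8 | 95.1% (difference 139.2) | 4.7% |

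Each withdrawal at 24 h with a 2-point error shifts the mean by 72 × 2 / 40 = 3.6 units. Seven such withdrawals cost 25.2 units (power 90.0%). Eight cost 28.8 (power 88.3%).

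Withdrawals in the other arm offset the bias. Take the high case of three in the EXPAREL arm. With one matching withdrawal under bupivacaine the net shift is 7.2 units, and the 4.7% becomes 3.8%. With two it is 3.6 units and 3.1%.

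These figures use the complete-data SE and leave out the between-imputation variance that Rubin's rules add.

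**5. Safety.** The only scheduled call in the protocol is the one in 9.2: "A follow-up phone call will occur on Post-operative Day (POD) 14". Section 13.11 has that call ask about new AEs. Under 13.8, Cohort 1 stays in the facility to 168 h and Cohort 2 to 96 h, so a telephone call during the first 96 h would be a call to an inpatient. The natural reading is that the final safety call is the POD 14 call, which leaves no gap in planned contact.

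**The case against.** Four points on the other side have force.

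- **Withdrawal does more than stop observation.** Protocol 11.6.3 bars other analgesics for 96 h, bars patient-controlled analgesia and dexmedetomidine, and bars local anaesthetic near the block through POD 7. Withdrawal frees a bleeding or septic subject from those limits. It would be wrong to say that it ends observation and nothing else. This stands, and the fix has to allow for it.
- **The termination score helps.** Section 10.3.3 requires a current-pain score. Under SAP section 5 an unscheduled score can fill a visit window, so it can enter the imputation model and carry some of the complication's effect on pain. This stands in part: one score cannot describe up to 72 h of later pain, and a gap of 1 to 2 points may be generous.
- **Continued scores are not a complete cure.** SAP 9.2.2 replaces scores for opioid use only. Scores after a repeat block or other non-opioid rescue could be misleadingly low. This stands, and such scores need a flag.
- **Few subjects may be affected.** The examples in 10.3 are excessive bleeding and acute sepsis, and no document shows that able, willing subjects would be withdrawn in any number. This also stands. Section 11.3.3 allows replacement for incomplete efficacy data, but that restores precision and does not remove bias.

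A reader might also infer from 10.3.2 that AE follow-up after withdrawal is optional throughout the protocol, or that 11 to 13 days of AE data could go uncollected. The documents do not support either reading. Section 14.1.2 requires AEs to be recorded through POD 14, 10.3 requires follow-up of ongoing AEs, 14.2.2 covers SAEs to POD 14, and 10.3.3 requires the final call.

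**Conclusion.** The point holds as a cheap improvement with a small expected effect. Section 10.3 reaches subjects who can still report pain, nothing continues the scheduled NRS to 96 h after withdrawal, and the primary analysis then relies on missing at random for these subjects, using NRS values alone.

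Under the assumed range, one arm's mean AUC is understated by 0.6 to 10.8 units and power stays at 95.1% or above. The upper end, with its 4.7% chance of false superiority, needs three withdrawals in the EXPAREL arm at 24 h, each 2 points wrong, and none under bupivacaine. A reader might take this as a threat to the primary conclusion. The documents do not support that: they give no withdrawal rate, and it would take 8 of 40 such withdrawals under bupivacaine to bring power below the stated 90%.

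On safety, the finding is a conflict between 10.3.2 and 14.1.2 and an undated call. Little safety data is likely to be lost.

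**What to change.** - **10.3 and 10.3.1:** end follow-up only for subjects unable or unwilling to continue, and use the same verb in both sections. Allow release from the 11.6.3 restrictions where care requires it, and record any such rescue.
- **10.3.3:** continue scheduled NRS and analgesic recording to 96 h for subjects able and willing. State that the final safety call is the POD 14 call in 13.11.
- **10.3.2:** make AE follow-up of dosed subjects through POD 14 mandatory unless consent to follow-up is withdrawn, to match 14.1.2.
- **SAP 9.2.2:** flag scores taken after non-opioid rescue and say how they will be handled.

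The cost is a few sentences in an amendment and a little extra data collection from the few who withdraw. The NRS schedule, e-diary and POD 14 call already exist, and the planned sample size need not change. The change recovers little from subjects who refuse further contact or are too ill to answer.

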10.3.3. Early Termination Assessments

In case of early termination, the following assessments shall be performed:

- Record date and time of withdrawal
- Record responses to pain assessment:
 - Pain intensity scores on the Numeric Rating Scale (NRS) measured as “How much pain are you experiencing right now?”
 - Pain intensity scores (using the NRS) measured as “What was your worst pain in the last 24 hours?”
 - Pain intensity scores (using the NRS) measured as “What was your average pain in the last 24 hours?”
- Remind to return the e-diary (if applicable)
- Final phone call for safety

11. TREATMENTS

11.1. Treatments to be Administered

Cohort 1: PK, PD, Efficacy, and Safety

The participants enrolled in Cohort 1 will provide blood samples for PK and measures for efficacy and safety. About 60 subjects undergoing bunionectomy will be enrolled in this cohort. On the day of surgery, eligible subjects will be randomized (1:1:1) to receive EXPAREL (n=20), EXPAREL admixed with 0.25% bupivacaine HCl (n=20), or 0.25% bupivacaine HCl (n=20) as a combined sciatic (in the popliteal fossa) and saphenous (in the adductor canal) nerve blocks.

Cohort 2: Efficacy and Safety

The participants enrolled in Cohort 2 will provide measures for efficacy and safety. About 60 subjects will be enrolled in this cohort. On day of surgery, eligible subjects will be randomized 1:1:1 to receive EXPAREL (n=20), EXPAREL admixed with 0.25% bupivacaine HCl (n=20), or bupivacaine HCl (n=20). All subjects will receive combined sciatic (in the popliteal fossa) and saphenous (in the adductor canal) nerve blocks, by stratifying by each surgery grouping.

Treatments for Cohort 1 and Cohort 2

On the day of surgery, Cohort 1 and 2 subjects will receive ultrasound-guided combined sciatic (in popliteal fossa) and adductor canal nerve block with one of the following treatments:

- **EXPAREL arm:** subjects randomized to this treatment arm will receive 20 mL (266 mg) EXPAREL mixed with 20 mL saline
- **EXPAREL admix arm:** subjects randomized to this treatment arm will receive 20 mL (266 mg) EXPAREL admixed with 20 mL (50 mg) 0.25% bupivacaine HCl
- **Bupivacaine HCl arm:** subjects randomized to this treatment arm will receive 40 mL (100 mg) 0.25% bupivacaine HCl

Block Procedure:

Subjects may be lightly sedated with 1 to 2 mg of midazolam IV before the block procedure. The study drug (EXPAREL, EXPAREL admixed with 0.25% bupivacaine HCl, or 0.25% bupivacaine HCl) will be administered under ultrasound guidance 90 min (\pm 30 min) prior to surgery.

For all arms, the total volume (40 mL) will be split such that 20 mL will be administered as the sciatic nerve block (in popliteal fossa) and 20 mL will be administered as the saphenous nerve block (in the adductor canal).

